Specific hypotheses: *Hypotheses 1.1 and 2.1 (neuropsychiatric outcomes)*. Following DAA therapy and obtaining a sustained viral response (SVR), 1.1: participants will show improved neuropsychiatric outcomes (e.g., cognitive function, fatigue, mood), as compared to baseline (pre-DAA therapy). 2.1: participants without AUDs will show greater improvement in neuropsychiatric outcomes than participants with AUDs. *Hypothesis 1.2 and 2.2 (neuroimaging outcomes)*. Reduced fractional anisotropy (FA) will be observed in the tracts that connect regions between which there is decreased functional connectivity. 1.2 and 2.2: Disintegrity within white matter tracks [as measured by FA and mean diffusivity (MD)] observed at baseline visits will be improved following DAA therapy, with greater improvement observed in participants without AUDs. On the fMRI Balloon analogue risk task (BART) and Monetary incentive delay task (MID), adults with HCV will be significantly more likely to display more impulsivity during the baseline visit, as compared to the post-DAA therapy visit. It is hypothesized that AUD may attenuate the positive antiviral therapy effects on impulsivity. *Hypothesis 1.3 and 2.3 (immune activation profile)*. Inflammatory profiles will be associated with neuropsychiatric impairments and alterations in white matter integrity and cortical activity. Following DAA therapy and obtaining an SVR, 1.3: participants will show reduced immune activation profiles (i.e., restored T cell phenotypes and a reduced inflammatory profile), as compared to baseline, and 2.3: participants without AUDs will show greater a reduction in inflammatory factors than participants with AUDs.

Scientific Rationale and Significance

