potential interaction of these factors—after possibly controlling for other subject-level covariates that remain constant (or nearly so) over the six months (e.g., age, sex, HCV genotype). Variables that could meaningfully vary over time (e.g., TFLB score, CIWA-Ar score) will be summarized in terms of a difference and then included as a covariate. Number of DAA therapy provider contacts will be included as an extra covariate that counts total contacts. All models will use “robust” (sandwich estimators) of variance to guard against potential misspecification of the underlying distribution of change scores or due to non-constant variance among the groups (Long and Ervin, 2000). The AUD \times HCV interaction will be assessed first in all models fit, and will be removed from the model only if evidence suggests ($p > 0.10$) these two factors don’t modify one another; otherwise, subsequent comparisons of each separate effect will be made within each level of the other (e.g., effect of HCV separately characterized for those with and then without AUD).

A supervised and directed approach will be taken in the exploratory analysis of inflammatory biomarkers. Principal component analysis (PCA) will be used to reduce the collection of ~12 correlated immune factors to a smaller number of uncorrelated linear combinations (the principal components) of biomarkers [e.g., (Bowman et al., 2012)]. Each component of this reduced set of uncorrelated patterns of inflammatory expression will be subjected to the same general linear models described earlier to determine whether AUD, HCV or AUD \times HCV are associated with it, even after adjustment for other covariates. If the overall test of association in the linear model shows significant ($p < 0.10$, for initial screen) variation among the groups, then separate models will be conducted on those biomarkers that most heavily contribute/dominate the principal component being screened. In this way, we may identify combinations of markers that are sensitive to AUD and HCV treatment outcomes, particularly CNS function.

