Neuroimaging measures. We will use the methods of the Fair Laboratory (Miranda-Dominguez et al., 2014) to analyze the rsMRI scans. We will use an ROI-to-ROI approach to calculate connectivity in the pre-processed data, based on the a priori regions previously associated with alcohol effects. Bivariate correlations between the average (BOLD) signal from these regions provide connectivity estimates. Several sources of spurious variance along with their temporal derivatives are then removed from the data through linear regression (e.g., signal from ventricular regions and signal from the white matter). The magnitude of connectivity changes between groups will be compared utilizing two-tailed t-tests. The raw p-values will be corrected for multiple comparisons and thresholded at a false discovery rate (FDR) correction of PFDR < 0.05 . Data from discounting tasks will be fit to equations using a softmax procedure (Miedl et al., 2012). We calculate the fractional areas under the discounting curves as impulsivity measures.

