Power. We estimated group size using fmripower (Mumford and Nichols, 2008). The MATLAB-based program calculates a power estimate given the between-group and within-subject error terms associated with a two tailed t-test of regression coefficients. The results suggested that 30 subjects (male and female) per group would yield a power of 0.8 for the test comparison. This sample size yields an 80% chance for us to identify AUD \times HCV interaction effects of 0.91 standard deviation (SD) or larger at the 0.10 level of significance. Use of the higher alpha-level is done to lessen the chance of making a type II (overlook) error and mistakenly omitting this term from the model. We also have 80% power for a 0.05-level test to detect any main effect, for either AUD or for HCV, of at least 0.51 SD in size. **Table 2** shows the smallest average change (between post- and pre-DAA therapy) among groups that would be of practical interest and the subsequent main effects (AUD+ vs AUD-; HCV+ vs HCV-) and interactions that derive from these minimally relevant average changes. The anticipated SD for the change scores was derived from reported SDs of each outcome supported by literature, and then converted to a SD for the difference assuming a modest correlation of 0.60 between pre- and post-DAA responses within the same subject. The principal comparisons proposed in this work parallel those in our preliminary work, and we were able to readily demonstrate differences in planned comparisons between the groups. Therefore, the proposed 30 subjects per group should provide us with sufficient power to test the predictions, anticipating that a small number of participants with HCV may not achieve SVR (n = ~3-6).

Table 2. Statistical power to evaluate antiviral therapy outcomes of significant clinical impact

Response/outcome	SD(diff)	Treatment group ^a			Effects and Power ^b			
		AUD-/HCV-	AUD-/HCV+	AUD+/HC V-	AUD+/HCV+	AUD main	HCV main	Interact.
Cognitive performance^c								
Attention	2.25	3.5	3.7	1.2	3.5	-1.25 (0.85)	1.25 (0.85)	2.1 (0.81)
Memory	2.50	3.0	3.4	0.4	3.0	-1.50 (0.91)	1.50 (0.91)	2.2 (0.78)
Executive function	1.80	2.0	2.1	0.3	2.0	-0.90 (0.78)	0.90 (0.78)	1.6 (0.78)
Behavioral response								
Impulsivity (BART/MID) ^d	1.35	0	-0.2	-0.1	-1.5	-0.70 (0.80)	-0.80 (0.90)	-1.20 (0.78)
Alcohol use (TLFB)	18.9	0	-1.0	-18	-36	-26.5 (0.99)	-9.50 (0.78)	-17.0 (0.79)
Mental health								
Depression (BDI)	4.0	0	-3.5	-2.7	-11.0	-5.1 (0.99)	-5.9 (0.99)	-4.8 (0.94)

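### Stated main-effect power (0.51 SD at 0.05) is for a test reached only if AUD × HCV is dropped; Table 2's cognitive means give Hypothesis 2.1's own contrast about 6–9% power

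*Combined protocol and SAP*

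**What the plan says.** Under Statistical analyses and power (Neuropsychiatric and laboratory measures), change scores are modelled on AUD, HCV and their interaction. The interaction is tested first and "will be removed from the model only if evidence suggests ($p > 0.10$) these two factors don’t modify one another". For the case where the term stays in, the rule is: "otherwise, subsequent comparisons of each separate effect will be made within each level of the other". No significance level, multiplicity rule, detectable effect or power is given for those within-level comparisons.

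The Power paragraph sets the interaction at level 0.10 to reduce the risk of "mistakenly omitting this term from the model". It then claims "80% power for a 0.05-level test to detect any main effect, for either AUD or for HCV, of at least 0.51 SD". Table 2 prints power for each AUD and HCV main effect and for the interaction. Footnote b gives 0.05 and 0.10 as the levels. Neither place says that the main-effect test depends on the interaction having been dropped. The paragraph concludes that 30 per group is enough to test the predictions.

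Hypothesis 2.1 (Specific hypotheses) is framed as change following DAA therapy and SVR: "participants without AUDs will show greater improvement in neuropsychiatric outcomes than participants with AUDs".

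**The concern.** A reader of Table 2 will take the main-effect column as the power of the AUD and HCV results to be reported. By the plan's own rule, a different test is reported whenever the interaction is kept. It uses half the participants, and its level is not given.

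The rule also lets the interaction p-value choose the question. One branch reports AUD averaged over HCV+ and HCV−; the other reports AUD within each HCV group. Only HCV+ participants receive DAA therapy and can reach SVR, so H2.1 is about AUD within HCV+. If the averaged effect is read as the answer to H2.1, a difference that lies almost wholly among HCV− participants could be reported as support.

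**Working it through.** **Inputs.** From Table 2: SD(diff), the four group means, and n = 30 per group. Levels are 0.05 (main) and 0.10 (interaction), from footnote b. Tests are taken as two-sided; the Power paragraph describes its first calculation as "associated with a two tailed t-test of regression coefficients". No covariates or dropout. Powers use t with 116 df; detectable effects use the normal approximation.

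**Standard errors in SD units.** Averaged effect (60 vs 60): √(1/30) = 0.1826. Interaction: √(4/30) = 0.3651. Within-level effect (30 vs 30): √(2/30) = 0.2582.

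**The plan's figures reproduce.**
- Main effect: (1.960 + 0.842) × 0.1826 = 0.511 SD (stated 0.51).
- Interaction: (1.645 + 0.842) × 0.3651 = 0.908 SD (stated 0.91).
- Attention, AUD: [(1.2 + 3.5) − (3.5 + 3.7)]/2 = −1.25, power 0.855 (printed 0.85).
- Attention, interaction: (3.5 − 1.2) − (3.7 − 3.5) = 2.1, power 0.815 (printed 0.81).

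**How often the main-effect test is reached.** Interaction power at 0.10 is the probability that the interaction is kept. The last two columns concern AUD within HCV+, that is, AUD+/HCV+ minus AUD−/HCV+, divided by SD(diff).

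| Outcome | Interaction kept (printed) | AUD main power (printed) | AUD within HCV+, SD | Its power at 0.05 |
|---|---|---|---|---|
| Attention | 0.815 (0.81) | 0.85 | −0.2/2.25 = −0.09 | 0.063 |
| Memory | 0.774 (0.78) | 0.91 | −0.4/2.50 = −0.16 | 0.094 |
| Executive function | 0.781 (0.78) | 0.78 | −0.1/1.80 = −0.06 | 0.055 |
| TLFB | 0.789 (0.79) | 0.99 | −35/18.9 = −1.85 | 1.00 |
| BDI | 0.948 (0.94) | 0.99 | −7.5/4.0 = −1.88 | 1.00 |
| FSS | 0.828 (0.83) | 0.99 | −0.2/0.63 = −0.32 | 0.23 |
| T cells, DP | 0.292 (0.29) | 0.19 | 9/22.5 = 0.40 | 0.34 |
| T cells, DN | 0.607 (0.61) | 0.48 | −19/27 = −0.70 | 0.77 |

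On the first six rows the main-effect test is reached in about 5–23% of trials; on DP it is reached in 71%. Impulsivity (0.78) and immune factors (0.92) behave like the six if analysed by this model. They are not counted because the plan also describes other handling: "We calculate the fractional areas under the discounting curves as impulsivity measures" for impulsivity, and principal components for immune factors. FA and MD are imaging outcomes and are not counted.

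**The replacement test.** Its 80%-power effect is 2.802 × 0.2582 = 0.72 SD at 0.05, and (2.241 + 0.842) × 0.2582 = 0.80 SD at 0.025. At 0.51 SD one such test has power 0.50 at 0.05 and 0.39 at 0.025.

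**The whole procedure (simulation, about 10⁶ trials or more per setting).**
- AUD effect of 0.51 SD at both HCV levels, no interaction, within-level tests at 0.05: an AUD claim by either route has probability 0.81, against 0.79 for the averaged test alone.
- Table 2's means: an AUD claim by either route has probability 0.94–1.00 on the six outcomes.
- No true effects, within-level tests at 0.05: AUD false-claim rate 9.4% (4.9 points from kept and 4.5 from dropped interactions). Two within-level tests with no pretest give 9.7%.
- No true effects, within-level tests at 0.025: 7.4%, against 4.9% with no pretest, so about 2.5 points come from the switch.

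**H2.1 on cognition.** The averaged AUD effect is significant at 0.05 while AUD within HCV+ is not in 0.80 (attention), 0.81 (memory) and 0.73 (executive function) of trials.

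**TLFB change as covariate.** Using Table 2's TLFB means and SD, the standard error of the averaged AUD effect is 0.225 SD if TLFB change explains no within-group outcome variance. The detectable effect is then 2.802 × 0.225 = 0.63 SD. With partial correlation r it shrinks by √(1 − r²): 0.60 at r = 0.3 and 0.55 at r = 0.5.

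**The case against.** Testing the interaction first is a recognised strategy, and 0.10 is a reasoned choice. The retention rates are simply Table 2's interaction column, so the plan discloses them; only the consequence goes unstated. All of this stands.

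Four stronger readings are tempting, and the documents do not support them.

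- **The trial has 50% power where it claims 80%.** The 50% belongs to one within-level test in isolation. The full rule has about 0.81 power for a uniform 0.51 SD effect.
- **Every outcome is affected.** The DP row usually reaches the main-effect test, and DN keeps the interaction in only 61% of trials.
- **The interaction rule causes the low H2.1 power.** It does not. AUD within HCV+ is planned at 0.06–0.16 SD for cognition, and a test at 0.05 of a difference that small has little power under any rule.
- **0.51 SD fails after adjustment for TLFB change.** The loss depends on how much outcome variance TLFB change explains. Study 1 in Preliminary Studies found alcohol use correlated with depressive and PTSD symptoms, so r = 0 is the pessimistic end, at least for such outcomes.

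The false-claim rates rest on an assumed level because the plan gives none. At 0.05 the excess comes mainly from two unadjusted tests, not from the pretest.

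None of this supplies the missing level or power, or says which contrast answers H2.1.

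**Conclusion.** The concern holds in a limited form. On six outcomes the stated main-effect power and 5% level describe a test that the plan's own means lead to in only about 5–23% of trials. The tests that usually replace it have no stated level or power. The cost is not lost sensitivity to AUD in general. It is an unstated error rate (about 9.4% per outcome at an assumed 0.05 per test, 7.4% at 0.025) and an unstated detectable effect (0.72 or 0.80 SD).

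The most important consequence is for H2.1 on cognition. Power for AUD within HCV+ is about 6%, 9% and 6% for attention, memory and executive function, beside printed AUD powers of 0.85, 0.91 and 0.78. The printed figures therefore do not support the statement that the sample is sufficient for that prediction.

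This rests on Table 2's means and SDs, a common SD, 30 completers per group, no covariates, and reading H2.1 as a statement about HCV+ participants, which its reference to DAA therapy and SVR requires. Dropout or failure to reach SVR would lower the H2.1 figures further.

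**What to change.** 1. In the Power paragraph and Table 2, state that main-effect power is for the effect averaged over the other factor, without covariates. Add the within-level detectable effects (0.72 SD at 0.05, 0.80 SD at 0.025) and the power of AUD within HCV+ for each outcome.
2. Name AUD within HCV+ in advance as the H2.1 contrast. Estimate it from the model that keeps AUD × HCV, test it at 0.05, and report it whatever the interaction p-value. Report the interaction with its confidence interval. Treat the averaged effects and the other within-level contrasts as secondary, with a stated level. Do not read the averaged AUD effect alone as support for H2.1. The H2.1 contrast need not share a multiplicity adjustment with the other three within-level contrasts, which would lower its power further.
3. If sensitivity after adjustment for TLFB change is quoted, give the range (0.63 SD at r = 0, 0.60 at 0.3, 0.55 at 0.5), not one figure.

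The cost is wording only, with no extra participants. The price is a less favourable stated sensitivity: the plan would have to say openly that H2.1 is barely powered for cognition under its own planning means.

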Comparison groups of adults with: i) active AUD and no HCV (n = 30) and ii) no AUD or HCV (n = 30) will also be studied. Thus, we will enroll 120 participants into the following four study groups: 1) AUD+/HCV+, 2) AUD-/HCV+, 3) AUD+/HCV- and 4) AUD-/HCV-. Evaluations will incorporate neuropsychiatric assessments, brain imaging [resting state (rs) magnetic rsMRI, functional (f) MRI (fMRI), and diffusion tensor imaging], and laboratory methods [e.g., multicolor flow cytometry, quantitative polymerase chain reaction (PCR), and multiplex immunoassays] to assess the interactive effects of alcohol use on brain and immune function [e.g. changes in T cell response and inflammatory cytokines, such as TNF- α] that contribute to viral persistence and neuropsychiatric impairments. We will use general linear models to assess whether average change in the response (e.g., neuropsychiatric and immunologic outcomes) over six months between post- and pre-DAA therapy for each subject differs among the four groups—either due to AUD, HCV, or the potential interaction of these factors—after controlling for other subject-level covariates that remain constant (or nearly so) over the 6 months (e.g., age, sex). Variables that could meaningfully vary over time (e.g., TLFB score) will be summarized in terms of a difference and then included as a covariate.

Table 1. Overview of human subjects procedures, including research visits and HCV treatment schedule^a (as per standard of care)

Weeks					
-2	0	12	18	24	26
Baseline visits (wks -2-0)^c		DAA therapy completion (wk 12)	- Check-in w/participants ^b	SVR assessment (wk 24; 12-wk post DAA therapy)	
- Clinical interview		ETR assessment (wk 12)		6-month follow-up visits (wks 24-26)^c	
- Neuropsychiatric assessment		- Check-in w/participants ^b		- Neuropsychiatric assessment	
- Specimen collection				- Specimen collection	
- Neuroimaging evaluation		DAA therapy initiation (wk 0)		- Neuroimaging evaluation	

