Diffusion-Weighted Imaging: DTI preprocessing will be performed using the DTI preprocess script (Takuya Hayashi, Center for Life Science Technologies, RIKEN, Kobe, JP) for FSL [(Smith et al., 2004) FMRIB, Oxford]. Scans will be corrected for eddy current distortion and motion. B_0 inhomogeneity distortion will be corrected using a B_0 field map (magnitude and phase) in FSL's fugue. DTI estimates (FA, λ_{1-3} , V_{1-3} , MD) will be calculated using DTIFIT. Voxelwise statistical analysis will be performed with TBSS (Smith et al., 2006) and nonlinear registration to the FMRIB58_FA common space will be conducted. Each subject's aligned FA data will be projected onto a mean skeleton. Voxelwise cross-subject statistics will be performed with FSL's *Randomise* with threshold-free cluster enhancement (TFCE).

Voxel-Based Morphometry: Structural images will be analyzed with FSL-VBM (Douaud et al., 2007) an optimized VBM protocol (Good et al., 2001) carried out with FSL (Smith et al., 2004). Images will be brain-extracted and tissue segmented, registered to the MNI-152 standard space using non-linear registration (Andersson et al., 2007), and flipped along the x-axis to create a left-right symmetric, study-specific gray matter template and modulated with a voxel-wise division by the Jacobian determinant of the non-linear transformation matrix to correct for local expansion or contraction. The modulated gray matter images will be smoothed with an isotropic Gaussian kernel with a sigma of 3 mm (FWHM = 7 mm). Group contrasts will be tested with FSL's *Randomise*, a permutation-based non-parametric procedure.

Statistical analyses and power. Statistical analyses for the project will be performed by the research team and the Biostatistics and Design Program at OHSU. All data sent to OHSU for statistical analysis will be coded.

Neuropsychiatric and laboratory measures. We plan to calculate the change in the response over six months between post- and pre-DAA therapy for each subject and use general linear models (GLMs) to assess whether average change differs among the four groups—either due to AUD, HCV, or the

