Expected outcomes and alternative considerations. Results are expected to determine the extent of improvement in CNS function (including neuropsychiatric outcomes) that is gained by successful completion of DAA therapy and whether or not co-morbid AUDs affect HCV treatment outcomes. Our hypotheses would be supported by finding improved CNS function following successful completion of DAA therapy (*i.e.*, obtaining an SVR), including: i) increased FA in the tracts that previously connected regions between which there was decreased functional connectivity, ii) improved functional connectivity, iii) reduced impulsivity, and iv) improved cognitive abilities. Following DAA therapy, these changes in CNS function will be associated with reduced peripheral immune activation. Individuals with active AUDs and HCV may show attenuated benefits in CNS function and immune response, post-DAA therapy. In participants with HCV and co-morbid AUDs, cumulative disruptions in cerebral connectivity that result from anatomical disruptions may contribute to persistent cognitive deficits and elevated inflammatory profiles. Alternatively, it is possible that floor effects for some of the variables (e.g., BDI-II scores) may limit our ability to detect significant improvements. However, cognitive performance benefits have been reported following IFN-based therapy for HCV (Kraus et al., 2013, Kuhn et al., 2017), and we have observed improvements in depression and fatigue in patients who obtained SVR (Huckans et al., 2015). It is also possible that differences in the number of DAA therapy provider visits between participants in the HCV+ and HCV- groups may affect neuropsychiatric outcome variables (e.g., alcohol use behavior). To assess the impact of this potential confound, we plan to include that characteristic as an extra covariate. Because CNS recovery may continue beyond the SVR assessment timepoint, patients who agree to participate in the study will be asked to allow our research team permission (via the informed consent process) to contact them for future follow-up investigation, which is beyond the scope of this current protocol. We also considered the potential concern that there may be a lack of research participants with HCV (given the pace at which the VA is treating HCV); however, estimates indicate that by 2020, there will still be ~560,000 adults with HCV in the US (Chhatwal et al., 2016).

Table 3. Project timeline

Year 1	Year 2	Year 3	Year 4

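### Resting-state connectivity change is compared by unadjusted t-tests between unnamed groups, so the AUD × HCV interaction is not tested for this outcome

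*Combined protocol and SAP*

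**What the plan says.** All references are to the combined protocol and SAP.

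- **Neuropsychiatric and laboratory measures** (under Statistical analyses and power): a general linear model is fitted to each participant's change score "to assess whether average change differs among the four groups", with AUD, HCV and their interaction, subject-level covariates and sandwich variances. The "interaction will be assessed first in all models fit" and is dropped only if p > 0.10. If it stays, each factor is compared within levels of the other.
- **Neuroimaging measures** (the paragraph that covers resting-state MRI): correlations between a priori regions give the connectivity estimates. The group comparison is one sentence: "The magnitude of connectivity changes between groups will be compared utilizing two-tailed t-tests". The p-values are then "thresholded at a false discovery rate (FDR) correction of PFDR < 0.05". The paragraph does not refer back to the linear model and does not give the number of ROI pairs.
- **Research Design and Methods, Overview**: the evaluations, resting-state MRI included, are meant "to assess the interactive effects of alcohol use on brain and immune function".
- **Expected outcomes and alternative considerations**: "ii) improved functional connectivity" is listed among the findings that would support the hypotheses.
- **Power**: "We also have 80% power for a 0.05-level test to detect any main effect, for either AUD or for HCV, of at least 0.51 SD"; for the interaction the figure is 0.91 SD at the 0.10 level. Table 2 has no connectivity row. Its imaging rows are FA and MD.

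**The concern.** The HCV-negative groups are there to separate what belongs to HCV and its cure from what belongs to alcohol. For connectivity, that means asking whether the AUD+ versus AUD− difference in change is larger or smaller in HCV+ than in HCV− participants. The plan has a model that asks this and uses it for other change scores. For connectivity it states a different test, without the interaction, the covariates or the robust variance.

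Two things are at stake. The interactive question in the Overview has no specified test for this outcome. And because the groups are not named, an analyst could choose anything from one comparison to all six pairs of the four groups, with very different sensitivity.

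**Working it through.** **1. What the t-tests can estimate.** Read the sentence as referring to pre-to-post change, and write m(AUD,HCV) for the mean change in a group.

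- Interaction: [m(+,+) − m(−,+)] − [m(+,−) − m(−,−)]. It uses all four means with weights +1, −1, −1, +1.
- Pairwise t-test, for example within HCV+: m(+,+) − m(−,+). This is one bracket only.
- Marginal t-test for AUD: ½[m(+,+) + m(+,−)] − ½[m(−,+) + m(−,−)]. This averages the two brackets.

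Neither kind of t-test gives the difference between the brackets. Two pairwise tests side by side do not give it either, since one being significant and the other not is not a test of their difference.

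**2. The plan's own figures.** Inputs from Power and the Table 2 footnotes: 30 per group, N = 120, change-score SD set to 1, two-sided alpha 0.05 for main effects and 0.10 for the interaction. Power is from the noncentral t.

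- Main effect, 60 vs 60: SE = √(2/60) = 0.183; 0.51/0.183 = 2.79; df 116. Power is 0.79 and the effect detectable at 80% power is 0.516 SD (0.511 by the normal approximation). The stated 0.51 reproduces.
- Interaction: SE = √(4/30) = 0.365; 0.91/0.365 = 2.49; df 116, alpha 0.10. Power is 0.80 and the detectable effect is 0.913 SD (0.908 normal). The stated 0.91 reproduces.

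**3. The connectivity t-tests under each reading.** Two-sided alpha 0.05, before FDR.

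| Reading | SE | df | Power at 0.51 SD | Detectable at 80% |
|---|---|---|---|---|
| Pairwise, 30 vs 30 | √(2/30) = 0.258 | 58 | 0.49 | 0.74 SD |
| Margins, 60 vs 60 | √(2/60) = 0.183 | 118 | 0.79 | 0.52 SD |

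In the marginal reading the other factor is left in the error term. If that factor has an effect of 0.51 SD (an assumption), the error SD becomes √(1 + 0.51²/4) = 1.03 and power falls only to 0.77.

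**4. FDR.** The number of ROI pairs is not given, so the per-test threshold is unknown. At an illustrative per-test alpha of 0.005 (an assumption), power at 0.51 SD is 0.48 for 60 vs 60 and 0.18 for 30 vs 30. FDR lowers sensitivity whichever model is used.

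**The case against.** **The linear model may already cover imaging.** The Overview gives neuropsychiatric and immunologic outcomes only as examples of the model's responses, just after listing brain imaging, and the interaction rule is worded for all models. This is a fair reading of the general text. But the specific neuroimaging sentence states a different test, and an analyst would follow that sentence. On this reading the two places conflict and the same correction is needed.

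**The power text mentions a t-test of regression coefficients, which could be an interaction test.** It could. That phrase describes what the imaging power program computes, with no design matrix or contrast given, and the analysis sentence does not take it up.

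**Aim 2 can be answered without the interaction.** This stands in large part. The Aim 2 hypotheses predict greater improvement after therapy in participants without AUD, and only HCV+ participants receive the therapy. A t-test of change between AUD+/HCV+ and AUD−/HCV+ addresses that. A reader might infer that the connectivity analysis cannot serve Aim 2 at all; the documents do not support this. What is missing is the control for AUD-related change in people without HCV.

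**Pairwise tests are not always weaker.** This also stands. If the interaction is retained, the linear model itself makes within-level comparisons of 30 vs 30. From Table 2's FA means and SD, the AUD difference within HCV+ is 0.019/0.02 = 0.95 SD, for which a 30 vs 30 t-test has power 0.95. The same inputs give 0.85 for the AUD main effect (0.011/0.02 = 0.55 SD) and 0.70 for the interaction (0.016/0.02 = 0.80 SD, alpha 0.10). The table prints 0.91 and 0.78 for the last two; the order is the same.

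**Conclusion.** The point holds for resting-state connectivity. Under a pairwise or a marginal reading of the t-test sentence, the AUD × HCV interaction goes untested for an outcome on which the hypotheses rely, and the groups to be compared are left open.

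The cost in power is conditional. If the tests are 30 vs 30, power at 0.51 SD is about 0.49 rather than 0.79, and the detectable difference about 0.74 rather than 0.52 SD. If they are 60 vs 60, power is essentially kept. All of this assumes 30 analysable participants per group and a single test at alpha 0.05.

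Two further inferences should be resisted. One is that the stated 0.51 SD sensitivity is simply lost: the plan gives it as a general single-test figure, never for connectivity, and FDR would erode it under the linear model too. The other is that connectivity alone departs from a model used for every other outcome: the diffusion and voxel-based morphometry analyses are planned with permutation testing in Randomise.

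**What to change.** Replace the t-test sentence in Neuroimaging measures with a statement along these lines:

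- For each ROI pair, the post-minus-pre connectivity change is fitted with the change-score model already set out for neuropsychiatric and laboratory measures: AUD, HCV, AUD × HCV, the same planned covariates and robust variance, with the interaction assessed first.
- If the interaction is retained, within-level contrasts are reported, for example AUD+ versus AUD− within HCV+.
- The planned FDR < 0.05 is applied across ROI pairs within each named effect, and the number of ROI pairs is stated.

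A Fisher-z transformation of the correlations and a head-motion covariate are optional additions.

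The cost is a short change of text and slightly more analysis work; data and sample size stay the same. The change does not make the interaction well powered: about 0.91 SD is detectable at alpha 0.10 before FDR. At alpha 0.05, power for 0.91 SD is 0.70 and the detectable interaction is 1.03 SD. Interaction results for connectivity should be reported with intervals and read accordingly.
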